7.4. Laboratory Procedures

None

8. SUBJECTS COMPLETION/WITHDRAWAL

8.1. Completion Criteria

Subjects are considered to have completed the study if they:

- provided informed consent.
- are eligible.
- completed all visits

8.2. Withdrawal/Discontinuation from the Study

A subject will be withdrawn from the study for any of the following reasons:

- Subject death during the study period.
- Subject withdrawal of consent.
- Subject not compliant to protocol
- Subject lost to follow-up.
- Subject no longer meets eligibility criteria (e.g. the subject becomes pregnant).
- Subject develops significant or serious adverse events causing discontinuation of study lens wear.
- Subjects who have experienced a Corneal Infiltrative Event (CIE).
- Investigator's clinical judgment regarding the subject safety reasons (that it is in the best interest of the subject to stop treatment).
- Subject missed any study visit.
- Subject not compliant with study lens wear schedule.
- Subject not successfully dispensed due to lack of efficacy and safety including poor vision, poor comfort or unacceptable fit.

For discontinued subjects, the Investigator will:

- Complete the current visit (scheduled or unscheduled).
- Complete the Final Evaluation, indicating the reason that the subject was discontinued from the study.
- Record the spherocylindrical refraction with best corrected distance visual acuity.
- Collect used test article(s) (worn or brought to the visit) from the subject and discard them, unless otherwise stated in Section 7.2.
- Collect all unused test article(s) from the subject.
- Make arrangements for subject care, if needed, due to their study participation

An additional subject may be enrolled if a subject discontinues from the study prematurely.

In cases where a subject is lost to follow-up, every possible effort must be made to contact the subject and determine the reason for discontinuation/withdrawal. The measures taken to follow up must be documented including two written attempts and a certified letter (or equivalent) as the final attempt.

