2.3	Compliance	Confirm compliance with the prescribed	
		wear schedule.	
2.4	PRO (CLUE and	The subject will respond to the Follow-Up	
	MRD) Questionnaires	PRO (CLUE and MRD) Questionnaires.	
2.5	Subject Reported	Subjects will respond to a verbal open-ended	
2.6	Ocular Symptoms	symptoms questionnaire.	
2.6	Subjective Acceptance	Record whether the subject's distance and	
2.7	Entrance Distance and	near vision with the lenses is acceptable. Record the distance and near Snellen visual	
2.7		acuity (OD, OS, OU) to the nearest letter with	
	Near Visual Acuity	the study contact lenses in place.	
		For near measurements use the ETDRS	
		2000 Series Chart 1 or 2.	
2.0	Distance Osses	Perform a distance over-refraction OD and	
2.8	Distance Over- Refraction and	OS using loose lenses outside of the	
	Distance Visual Acuity	phoropter under ambient room illumination.	
	Distance visual Acuity	The distance over-refraction may also be	
		refined under binocular conditions.	
		Record the results. The results of the	
		distance over-refraction may also be checked	
		for the impact on near vision under	
		monocular and/or binocular conditions.	
2.9	Toric Fit Evaluation	Record:	
		The rotational position to the nearest	
		degree	
		Lens stability with blink	
		Toric fit acceptable or unacceptable	
		Toric lens fit will be unacceptable if lenses	
		rotated more than 30 degrees, or lens	
		stability is worse than 5 degrees movement	
		with blink. If toric fit is unacceptable,	

	Vi	sit 2: Treatment 1 Follow-Up 1	
Step	Procedure	Details	
		remove, store, and label the lenses, and	
		proceed to final evaluation.	
2.10	Lens Fit Assessment	Evaluate and grade lens centration, primary	
		gaze movement, upgaze movement and	
		tightness (push-up test).	
		The subject should not proceed to wear the	
		lenses if any of the following is observed:	
		• presence of limbal exposure (appearance	
		of clear cornea) in any gaze	
		• presence of edge lift	
		• presence of unacceptable movement (excessive or insufficient) in all three	
		movement categories (primary gaze,	
		upgaze, and push-up).	
		10 1	
		If either lens is deemed unacceptable, the	
		subject will be discontinued from the study.	
		Remove the lenses, perform a slit-lamp	
		evaluation, and complete the Final Evaluation form.	
2.11	Lens Power	If the subject's vision is unacceptable for at	
2.11	Modification (if	least one distance or the Investigator	
	required)	determines that the visual acuity or over-	

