		If either lens is deemed unacceptable, the subject will be discontinued from the study. Remove the lenses, perform a slit-lamp evaluation, and complete the Final Evaluation form.		
4.12.	Visual Performance Distance (4M) Intermediate (64 cm) Near (40 cm)	Visual performance will be recorded OD, OS, and OU for the following: Distance, Bright Illuminance ETDRS Charts 4M-HC#1, HC#2, HC#3 and LC#1, LC#2 and LC#3 Near, Bright Illuminance Reduced Guillon-Poling Charts High Contrast and Low Contrast Intermediate (64 cm) and Near (40 cm).		
		Distance, Dim Illuminance (with Distance goggles) ETDRS Charts 4M-HC#4, HC#5, HC#6 Near, Dim Illuminance (with Near goggles) Reduced Guillon-Poling charts High Contrast Intermediate (64 cm) and Near (40 cm). Note: The room illuminance must be between 7.3 and 7.9 EV.		

	Visit 4: Treatment 1 Follow-Up 3				
Step	Procedure	Details			
		 Distance, HC-1 Chart luminance Acceptable EV Range 10.5-10.7. Guillon-Poling, Near Chart Luminance Acceptable EV Range 10.8-11.1. Do not use the Mesopic filter for Dim luminance (Dim luminance will be simulated by using the goggles). 			
4.13.	Lens Removal	Have the subject remove the study lenses. Temporarily store the worn lenses until Biomicroscopy has been completed. If no adverse event or PQC was recorded, the worn lenses may be discarded.			

FINAL EVALUATION

The final evaluation will ordinarily take place immediately following the last scheduled follow-up visit per the study protocol. It may also take place at any point the subject discontinues the study or is terminated from the study.

	Final Evaluation				
Step	Procedure	Details			
F.1	Final Exam Form	Indicate if the subject completed the study successfully. If subject discontinued from the study, indicate the reason.			
F.2	Biomicroscopy	FDA Slit Lamp Classification Scale will be used to grade the findings and determine eligibility. If the clearance of the fluorescein needs to be expedited, preservative-free rewetting drops or saline may be instilled.			
F.3	Subjective spherocylindrical Refraction	An optimal, binocular balanced distance sphero-cylindrical refraction will be performed. Record the refraction and distance visual acuity (OD, OS, OU) to the nearest letter.			
F.4	Exit Distance Visual Acuity	Record the distance Snellen visual acuity (OD, OS, OU) to the nearest letter, and the type of visual correction being worn (habitual lenses, distance spectacles or unaided).			

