7.3. Unscheduled Visits

If, during the investigation, a subject requires an unscheduled visit to the clinical site, the following information will be collected at a minimum:

- Chief complaint prompting the visit. If the reason is an adverse event, the applicable eCRF for the adverse event must be completed and subject record completed as appropriate
- Date and time of the visit and all procedures completed at the unscheduled visit
- Review of adverse event and concomitant medications
- Documentation of any test article dispensed or collected from the subject, if applicable
- Slit lamp findings (using the Slit Lamp Classification Scale)

If the Investigator withdraws a subject from the study, the final study visit case report forms must be completed indicating the reason(s) why the subject was withdrawn. The subject record must be completed documenting the date and primary reason for withdrawal and the study CRA notified.

Any ocular and non-ocular Adverse Events that are ongoing at the time of the study visit will be followed by the Investigator, within licensure, until they have resolved, returned to pretreatment status, stabilized, or been satisfactorily explained. If further treatment i.e., beyond licensure is required, the subject will be referred to the appropriate health care provider.

The following information will be collected during an unscheduled visit.

	Unscheduled Visit				
Step	Procedure	Details			
U.1	Reason for	Indicate if the only reason for the visit is that			
	unscheduled visit	the subject requires additional test articles. If			
		the reason is other than resupply of			
		previously dispensed lenses, specify the			
		reason for the visit.			
U.2	Chief Complaints (if	Record the subject's chief complaints for			
	applicable)	reasons for the unscheduled visit.			
U.3	Adverse Events and	Review any changes to the subject's medical			
	Concomitant	history or concomitant medications from the			
	Medications Review	previous study visit. Record any changes, and			
	(if applicable)	any adverse events.			
U.4	Entrance VA (if	Record the distance Snellen visual acuity			
	applicable)	(OD, OS, OU) to the nearest letter, and the			
		type of visual correction being worn (study			
		lenses, habitual lenses, distance spectacles or			
		unaided).			
U.5	Subjective Sphero-	Perform bare-eye subjective spherocylindrical			
	cylindrical	refraction with a phoropter (adopt the			
	Refraction (if	maximum plus to maximum visual acuity			

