14. STATISTICAL METHODS

14.1. General Considerations

Statistical Analysis will be undertaken by the sponsor or under the authority of the sponsor. A general description of the statistical methods to be implemented in this clinical trial is outlined below.

All data summaries and statistical analyses will be performed using the Statistical Analysis System (SAS) software Version 9.4 or higher (SAS Institute, Cary, NC).⁸ Throughout the analysis of data, the results for each subject/eye will be used when available for summarization and statistical analysis. Unscheduled visits will be summarized separately and will be excluded from the statistical analysis.

Summary tables (descriptive statistics and/or frequency tables) will be provided for all baseline variables, efficacy variables and safety variables as appropriate. Continuous variables will be summarized with descriptive statistics (n, mean, standard deviation [SD], median, minimum and maximum). Frequency count and percentage of subjects or eyes within each category will be provided for categorical data.

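### A subject who stops before Visit 2 and comes back to exit gives no study-lens CLUE score, because neither exit route collects one

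*Combined protocol and SAP*

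**What the plan says.** Section 8.2 gives the exit procedure for a discontinued subject. The investigator is to "Complete the current visit (scheduled or unscheduled") and then "Complete the Final Evaluation, indicating the reason that the subject was discontinued from the study". Section 7.2 says of the Final Evaluation: "It may also take place at any point the subject discontinues the study or is terminated from the study".

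- **Final Evaluation (F.1 to F.4).** The steps are an exam form, slit lamp, refraction and Snellen distance acuity. For F.4 the site records the "type of visual correction being worn (habitual lenses, distance spectacles or unaided"). There is no CLUE step.
- **Unscheduled visit (section 7.3).** The text says "the following information will be collected at a minimum", and U.1 to U.10 cover reason, complaints, adverse events, Snellen acuity, refraction, slit lamp, dispensing and fit. There is no CLUE step here either.
- **Use of the data (section 14.1).** "Unscheduled visits will be summarized separately and will be excluded from the statistical analysis".
- **Scheduled CLUE.** The questionnaire is given at baseline (step 1.10) and at Visits 2, 3 and 4 (steps 2.4, 3.4 and 4.5). At Visit 2 the step is headed "PRO (CLUE and MRD) Questionnaires". The CLUE models in 14.5 and 14.6 take all four visits as events.
- **Missing data (section 14.9).** Nothing is imputed in the main analysis. Multiple imputation is a sensitivity analysis that runs only if dropout exceeds 15%.
- **Analysis set.** Section 14.3 limits the Per-Protocol set to subjects who completed all visits. Sections 14.5 and 14.6 do not say which set the CLUE models use.

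**The concern.** CLUE vision carries primary hypotheses 1 and 2, and CLUE vision, comfort and handling carry the secondary non-inferiority comparisons with the habitual correction. A subject who stops in the first week because vision, comfort or handling is poor has an unfavourable opinion of the study lens that bears directly on these endpoints. The plan can have that subject in the clinic for a slit lamp and refraction without asking the question. Appendix I, section 5.0 describes such a case: a subject who says by telephone that they wish to discontinue is told to stop wearing the lenses and return for a Final Evaluation.

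The baseline describes the habitual lens. If those who dislike the study lens leave unscored, the remaining subjects show a better change from baseline, and the error favours a non-inferiority claim. The score cannot be obtained once the subject has gone.

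**Working it through.** **1. Who loses what.** Setting the exit steps beside the visit schedule:

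| When the subject stops | CLUE scores available to the models |
|---|---|
| Between Visit 1 and Visit 2 | Habitual-lens baseline only |
| At Visit 2 | Baseline and Visit 2 (step 2.4 comes early in the visit) |
| Between Visit 2 and Visit 3 | Baseline and Visit 2 |
| At Visit 3, or between Visit 3 and Visit 4 | Baseline, Visit 2 and Visit 3 |

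Only the first row has no study-lens score.

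**2. Whether the sensitivity analysis would run.** Planned dropout from section 14.2:
- Myopes: 5/50 = 10%.
- Hyperopes: 5/40 = 12.5%.
- Overall: 10/90 = 11.1%.

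All are below 15%. The trigger needs at least 14 of 90 overall (8 of 50 myopes or 7 of 40 hyperopes, if applied by stratum). At the planned rate the multiple imputation is not done.

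**3. Size of bias in the change from baseline.** The plan gives no figure for this, so it is shown over an assumed range. With k first-week leavers among 40 hyperopes, each d points worse than completers, the completers' mean overstates the mean of all 40 by k × d / 40.

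| k | d | Overstatement (points) | Share of 5-point margin |
|---|---|---|---|
| 1 | 10 | 0.25 | 5% |
| 1 | 30 | 0.75 | 15% |
| 2 | 10 | 0.50 | 10% |
| 2 | 30 | 1.50 | 30% |

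This is an upper bound for each pair, because it ignores the baseline scores that the model retains.

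**4. What that does to the non-inferiority test.** Section 14.6 declares non-inferiority if the lower 95% limit is above -5, so the nominal error at a true change of -5 is 2.5%. Table 7 gives hyperope vision SDs of 14.71 (baseline) and 18.65 (2 weeks). The target is N = 35, and Table 9 uses correlations of 0.3 and 0.5.
- SD of change = √(14.71² + 18.65² − 2ρ × 14.71 × 18.65) = 19.99 (ρ = 0.3) or 17.03 (ρ = 0.5).
- Standard error = SD/√35 = 3.38 or 2.88.
- Error with a 0.25-point bias: about 3%.
- Error with a 1.5-point bias: 6.3% (ρ = 0.3) or 7.3% (ρ = 0.5).

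This is a paired t approximation to the mixed model.

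**5. Whether one study-lens score helps.** A simulation under assumptions that are not in the documents used 40 hyperopes, SD 18.65, correlation 0.5 and 100 runs; the five lowest Visit 2 scorers leave. Mean Visit 4 CLUE vision:
- Full data: 47.4.
- Completers only: 49.5.
- Mixed model keeping leavers' baseline only: 48.5.
- Mixed model keeping leavers' baseline and Visit 2 score: 47.5.

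One study-lens score cuts the bias from about 1.1 to about 0.1 points. This is a favourable case, because leaving depends on the very score that is then observed.

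**6. Primary hypotheses 1 and 2.** Let all planned losses score 0.
- Hyperopes: 0.875 × 47.3 = 41.4, threshold 32.
- Myopes: 0.90 × 55.1 = 49.6, threshold 40.

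Both means remain more than 9 points above their thresholds.

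**The case against.** The strongest reply is that the affected group is small. Lenses are dispensed only if the subject finds vision and comfort acceptable (step 1.35), Visit 2 follows within 6 to 8 days, and lens power can be changed there. Subjects lost to follow-up would give no score under any fix. The earlier studies in section 1.5 lost few subjects: 37 of 40 myopes completed, and there were 2 discontinuations among 30 hyperopes enrolled. Section 14.9 adds that past trials give no evidence that dropout is systematic. All of this stands as a limit on size. It does not remove the gap, because lack of evidence for informative dropout is not evidence against it, and the plan does not collect the score that would show it.

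A second reply is that an early score in a lens not yet optimized is not a 2-week score. That is correct. It informs the Visit 4 mean only through the model's correlation. The CLUE wording and recall period are also not visible in Appendix A, so their suitability at early exit cannot be checked here.

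A reader might infer that early quitters add nothing to the CLUE endpoints. The documents do not support that: leavers after Visit 2 or 3 have study-lens scores in the four-event models, and even a first-week leaver contributes a baseline. It would hold only if the models were restricted to Per-Protocol completers, which 14.5 and 14.6 do not state.

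**Conclusion.** The point holds as a cheap improvement. A subject who stops before Visit 2 and attends the clinic to exit gives no study-lens CLUE, and no step in the plan supplies one. If such subjects leave because they dislike the lens, the change from baseline is biased towards non-inferiority. With 1 to 2 such hyperopes, 10 to 30 points worse than completers, the bias is at most 0.25 to 1.5 points against the 5-point margin. Both the count and the gap are assumptions; the documents do not give the timing of or reasons for past dropout.

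Two larger readings are tempting. Taking all five planned hyperope losses at 30 points gives 5 × 30 / 40 = 3.75 points, but that requires every loss, for any of the reasons in section 8.2, to be a dissatisfied first-week leaver. A reader might also want an exit logMAR measurement. The logMAR model in 14.5 uses 2-week data with position as its only specified fixed effect, so an early value would have no place in it. Primary hypotheses 1 and 2 are little affected.

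**What to change.** 1. **Final Evaluation (7.2).** For any subject leaving before Visit 4 who has worn study lenses since the last CLUE, give the follow-up CLUE before the exit examination.
2. **Section 14.1.** Exempt this early-exit CLUE record from the exclusion of unscheduled visits.
3. **Sections 14.5 and 14.6.** Assign the score to the next scheduled event (Visit 2, 3 or 4), and state that the CLUE models use all dispensed subjects with an observation, not only Per-Protocol completers. Without this the new record could be discarded. Naming the present ITT set would not be enough, since 14.3 defines it on randomized subjects and the study has one arm.

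No exit logMAR is needed.

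The cost is one existing questionnaire in at most about 10 subjects (the planned loss of 90 − 80), one eCRF branch, and short additions to 14.1, 14.5 and 14.6. The downside is that a few scores will be off schedule, some in lenses that have not been optimized, and some taken after wear has stopped. The report should list them with the exit date so that a reader can see how many there are.

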9. PRE-STUDY AND CONCOMITANT INTERVENTION/MEDICATION

Concomitant medications will be documented during screening and updated during the study. Disallowed medications and therapies are medications or therapies that contraindicate contact lens wear. See the Exclusion criteria for specific details.

9.1. Systemic Medications

Certain systemic medications are known to have a higher likelihood to interfere with contact lens wear, chiefly by disrupting the tear film. A summary of disallowed medications is shown in Table 4. Subjects with a history of taking these medications will be allowed to enroll only if:

• The medications have been taken on a continual or routine basis for at least 6 months and the subject has demonstrated successful contact lens wear during this time.

Or

• The subject previously used these medications on a temporary basis and has ceased that medication at least 1 week prior to signing the informed consent.

Table 4: Disallowed systemic medications

Class of Drug	Common Indication(s)	Common Examples
Anticholinergics	Irritable bowel syndrome, Parkinson's disease, peptic ulcer, cystitis, nasal congestion, cold symptoms, overactive bladder, COPD	Bentyl, Spiriva, Atrovent, Hyosyne, Levsin, Symax Fastab, Symax SL, Homax SL, Cogentin, Transderm Scop, etc.
Oral Phenothiazines	Antipsychotic disorders (schizophrenia, mania)	Compazine, Mellaril, Thorazine, Phenergan, etc.

Class of Drug	Common Indication(s)	Common Examples
Oral/Inhaled Corticosteroids	Arthritis, colitis, asthma, bronchitis, allergic or inflammatory conditions	Cortisone, Prednisone, Hydrocortisone, Medrol, Kenalog, Flonase etc.
Oral Retinoids	Seborrhea, acne	Isotretinoin, Acitretin, Alitretinoin, etc.
Oral Tetracycline	Urinary Tract Infection, acne, chlamydia, gonorrhea	Sumycin, Achromycin V, etc.

10. DEVIATIONS FROM THE PROTOCOL

Investigator will notify study sponsor upon identification of a protocol deviation. Protocol deviations must be reported to the sponsor within 24 hours after discovery of the protocol deviation. The Investigator will report deviations per IRB/IEC requirements. All deviations will be tracked, and corrective actions implemented as appropriate.

If it becomes necessary for the Investigator to implement a deviation in order to eliminate an immediate hazard to the trial subject, the Investigator may implement the deviation immediately without notification to the sponsor. Within 24 hours after the implemented deviation, the Investigator must notify and provide the rationale to the Sponsor and, as required, the IEC/IRB.

If the deviation potentially impacts the safety of patient or changes the technical integrity of the study, then it must be reported to IEC/IRB. This is a "Major Deviation". Deviations that contradict the information contained in the Informed Consent/Assent forms will be considered Major Deviations.

Minor deviations have no substantive effect on patient safety or technical integrity of the study. They are often logistical in nature.

Protocol waivers are prohibited.

Table 5 lists examples of deviations that will constitute major and minor protocol deviations for this study.

Table 5: Examples of major and minor protocol deviations

Deviation category	Major deviation	Minor deviation
Out-of-window visit	Visit attended 3 or more days out of visit window defined in study procedures	Visit attended 2 or fewer days out of visit window defined in study procedures
Insufficient wear of study lenses	Subject does not wear study lenses for at least 6 hours per day for 3 or more days between scheduled visits.	Subject does not wear study lenses for at least 6 hours per day for 2 days between scheduled visits.

11. STUDY TERMINATION

If more than 2 subjects in the investigational soft contact lens group develop serious expected (e.g., definite or probable MK) or unexpected device related adverse events, the study will be suspended. Upon review and consultation with IRB, DMC, and JJVC Safety Review committee, the study may be terminated. This potential stopping rule is established based on our trial involving approximately 200 subjects wearing the investigational soft contact lens for up to 3 years with an assumed MK rate that is below 0.2% per patient-year. The rate of 0.2% per patient year is the established rate for extended wear lenses in adults, which was requested by the FDA as a criterion for evaluating a contact lens for pediatric use in an FDA response to a pre-IDE submission. To be conservative, 200 independent patient years were used in the calculation. The probability of observing 2 cases or more incidents of MK is 0.061, and 3 cases or more incidents of MK is 0.007 (given an MK rate of 0.2% per patient year).

The occurrence of one or more Unanticipated Serious Adverse Device Effect (USADE), or any SAE where the relationship to study agent cannot be ruled out, may result in stopping further dispensing of test article. In the event of a USADE or SAE, the Sponsor may unmask the treatment regimen for the subject(s) and will discuss this with the Investigator before any further subjects are enrolled.

The Sponsor will determine when a study will be stopped. The Principal Investigator always has the discretion to initiate stopping the study based on patient safety or if information indicates the study's results are compromised.

JJVC reserves the right to terminate the study at any time for any reason. Additionally, the IEC/IRB reserves the right to terminate the study if an unreasonable risk is determined. The study can be terminated by the Principal Investigator at the individual clinical site due to specific clinical observations, if in their opinion, after a discussion with JJVC, it is determined that it would be unwise to continue at the clinical site.

JJVC (and the IEC/IRB and DMC, if applicable) will evaluate all adverse events. If it is determined that an adverse event presents an unreasonable risk, the investigation, or that part of the investigation presenting the risk, will be terminated as soon as possible.

Should the study be terminated (either prematurely or as scheduled), the Investigator will notify the IEC/IRB and Regulatory Authority as required by local regulatory requirements.

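### The Section 11 suspension threshold is justified with 200 patient-years of exposure; this trial has about 5.2, so the quoted microbial keratitis probabilities do not describe it

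*Combined protocol and SAP*

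**What the plan says.** Section 11 (Study Termination) sets one numerical threshold that makes suspension mandatory. If more than 2 subjects "develop serious expected (e.g., definite or probable MK) or unexpected device related adverse events, the study will be suspended". It states that the rule was "established based on our trial involving approximately 200 subjects wearing the investigational soft contact lens for up to 3 years", with an assumed MK rate below 0.2% per patient-year. On the source of that rate it says: "The rate of 0.2% per patient year is the established rate for extended wear lenses in adults", and adds that the FDA asked for it as a criterion for a lens intended for paediatric use. On exposure: "To be conservative, 200 independent patient years were used in the calculation". The result: "The probability of observing 2 cases or more incidents of MK is 0.061, and 3 cases or more incidents of MK is 0.007".

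The rest of the protocol describes a different study:

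- about 90 subjects, 50 myopes and 40 hyperopes, with about 80 completers (Section 4.1);
- ages 40 to 70 (Section 3.2);
- about 3 weeks per subject (Section 4.3), with a 21-day average dispensing period (Section 6.1);
- daily disposable wear (Synopsis).

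The sentence after the suspension rule reads: "Upon review and consultation with IRB, DMC, and JJVC Safety Review committee, the study may be terminated". Section 16.4 (Data Monitoring Committee) says a DMC is not applicable.

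**The concern.** The number of subjects, the follow-up, the exposure, the wear modality and the paediatric context behind the threshold all differ from this trial. The paragraph appears to have been carried over from a longer and larger study.

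The tail probabilities are there to show how often a threshold of three would be crossed by chance at the benchmark rate. With far less exposure, three MK cases at that rate become almost impossible, and even one would be notable. An IRB approving the protocol is thus shown properties of a safety threshold that this design does not have. The mismatch also runs in the permissive direction: overstated exposure makes a threshold of three look better matched to chance events than it is.

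The DMC wording is a separate and smaller matter. It names a review step that the study cannot carry out as written.

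**Working it through.** **Step 1. Reproduce the plan's figures.** Inputs from Section 11: 200 patient-years and 0.002 per patient-year, so the expected count is 200 × 0.002 = 0.4.

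- Binomial, n = 200, p = 0.002: P(≥2) = 0.0614 and P(≥3) = 0.0078.
- Poisson, mean 0.4: P(≥2) = 1 − e^(−0.4)(1 + 0.4) = 0.0616; P(≥3) = 1 − e^(−0.4)(1 + 0.4 + 0.08) = 0.0079.

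The stated 0.061 and 0.007 are recovered, the second being 0.0078 truncated rather than rounded. The nominal exposure of the trial that Section 11 describes, 200 × 3 = 600 patient-years, would give 0.337 and 0.120. The quoted figures therefore belong to 200 patient-years.

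**Step 2. Exposure in this trial.** Inputs: 90 subjects (Section 4.1) and 21 days (Section 6.1). The 7 ± 1 day windows between the four visits (Section 7.1, Table 3) allow 18 to 24 days.

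- Central: 90 × 21 / 365.25 = 5.17 patient-years; 200 / 5.17 = 38.7.
- 90 subjects, 18 to 24 days: 4.44 to 5.91 patient-years.
- 80 completers only, 18 / 21 / 24 days: 3.94 / 4.60 / 5.26 patient-years.

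**Step 3. Probabilities at the plan's own rate.** Poisson with mean = patient-years × 0.002:

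| Subjects × days | Patient-years | Mean | P(≥1) | P(≥2) | P(≥3) |
|---|---|---|---|---|---|
| 90 × 21 | 5.17 | 0.01035 | 0.0103 | 5.3e-5 | 1.8e-7 |
| 90 × 18 | 4.44 | 0.00887 | 0.0088 | 3.9e-5 | 1.2e-7 |
| 90 × 24 | 5.91 | 0.01183 | 0.0118 | 6.9e-5 | 2.7e-7 |
| 80 × 21 | 4.60 | 0.00920 | 0.0092 | 4.2e-5 | 1.3e-7 |

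For 80 completers at 18 days, P(≥1) is 0.0079; at 24 days it is 0.0105. A binomial with a per-subject probability gives the same picture (90 × 21: 0.0103, 5.3e-5, 1.8e-7).

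**Step 4. The rate at which the quoted figure would apply here.** P(≥3) = 0.0078 needs a Poisson mean of 0.398. Then 0.398 / 5.17 = 0.077, or about 7.7% per patient-year, some 38 times the benchmark.

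**Step 5. The DMC references.** The consultation sentence in Section 11 names a DMC without qualification. A later sentence in the same section, on evaluating adverse events, adds that the DMC is involved only if applicable. Section 16.4 says it is not. The qualifier is not attached to the consultation sentence.

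**The case against.** The strongest reply is that subject safety does not rest on this rule. Under Section 11, one unanticipated serious device effect, or "any SAE where the relationship to study agent cannot be ruled out, may result in stopping further dispensing of test article". The sponsor may terminate at any time, the investigator and IRB can also stop the study, and if an adverse event presents an unreasonable risk the investigation, "or that part of the investigation presenting the risk, will be terminated as soon as possible". Section 8.2 withdraws any subject with a corneal infiltrative event, and Section 13.4.1 requires serious and significant events to be reported within 24 hours. This stands, and it limits the consequence. It does not make the quoted probabilities right. The one-event halt to dispensing is also discretionary, whereas the numerical threshold is mandatory.

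Second, the trigger covers other serious expected and unexpected device-related events, so the MK-only probability is not the probability that the rule fires. That also stands. The documents give no rate for the other events, so the rule's overall chance of firing cannot be calculated. The plan's own justification, however, is given in MK terms alone.

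Third, 0.2% is an adult rate used as an upper benchmark, so keeping it is defensible. Agreed, provided the text says that it is borrowed from extended wear.

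Fourth, restating the probabilities leaves the threshold itself unsettled. This is fair. On the plan's own scale, the counterpart of 0.0078 here is P(≥1) = 0.0103, so one MK case in this trial is about as surprising as three in 200 patient-years. Whether the threshold should change is a clinical safety decision, and the safety group should have that comparison in front of it.

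Finally, the DMC mention blocks neither suspension nor termination. Agreed; it is editorial, and the main point holds without it.

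**Conclusion.** The concern holds. Section 11's arithmetic is right for its inputs, but the inputs describe a different trial. Exposure is overstated about 39-fold (5.2 against 200 patient-years). At 0.2% per patient-year the probabilities of at least 2 and at least 3 MK cases are about 0.005% and 0.00002%, against the stated 0.061 and 0.007.

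This assumes that all 90 enrolled subjects wear lenses for 21 days and that events are independent at a constant rate. Visit windows or counting completers only move P(≥1) between about 0.8% and 1.2%. Replacement subjects (Section 8.2) or the enrolment increase permitted in Section 14.2 would raise exposure slightly. None of this changes the conclusion. It is a real error in the rationale for a safety rule, cheap to correct and of limited practical consequence.

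**What to change.** In Section 11, replace the 200-subject, 3-year basis and its probabilities with text such as:

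> This trial will expose about 90 subjects for about 21 days each, about 5.2 patient-years. At a benchmark MK rate of 0.2% per patient-year, borrowed from extended wear in adults, the probability of at least 1, 2 and 3 MK cases is about 1.0%, 0.005% and 0.00002%.

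Have the sponsor's safety group confirm, with these figures before it, that more than 2 subjects is still the intended threshold. In the consultation sentence that follows the suspension rule, delete the DMC and leave the IRB and the sponsor's Safety Review committee.

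The restated figures correct the rationale; they do not give a 5-patient-year study the power to detect an MK risk. The cost is one paragraph and one confirmation. If the protocol is already approved, the change goes to the IEC/IRB as a protocol revision under Section 18.3. Enrolment, endpoints and data are unaffected.
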